2. INTRODUCTION

2.1. Study Rationale

AL101 is a potent and selective inhibitor of gamma secretase-mediated Notch signaling that is currently under development as monotherapy for the treatment of various cancer. A large body of experimental evidence supports the causal role of Notch pathway deregulation in cancer development and progression (Previs, 2015; Wang, 2015b; Braune, 2016; Vinson, 2016; Xiao, 2016; Zhao, 2017).

Triple negative breast cancer (TNBC) is a heterogeneous disease entity constituting about 15% of newly diagnosed breast cancer (BC) cases and a higher percentage of metastatic BC cases worldwide. TNBC is associated with poor prognosis and lack of sustained response to conventional chemotherapeutic agents (Rouzier, 2005; Dua, 2017; Polk, 2017). Patients with recurrent and/or metastatic TNBC have a median survival of approximately 13-24 months (Kassam, 2009; Steponaviciene, 2011); therefore, there is an urgent need to identify new therapeutic strategies for these patients.

The Notch pathway is activated during mammary gland development and has been implicated as a key driver in BC (Collu, 2007). The frequency of Notch mutations or gene rearrangement was reported at 5 to 16% in small cohorts of TNBC tumors and high level of Notch expression was associated with poorer overall survival (Robinson, 2011; Stoeck, 2014; Wang, 2015a). In addition, elevated Hes4 expression, a marker of Notch activation, is associated with poorer prognosis in TNBC (Stoeck, 2014).

In nonclinical models, AL101 has a broad-spectrum antitumor activity against solid tumor xenografts of diverse histological types at tolerable doses, including breast carcinoma. AL101 exerted its antitumor activity through direct inhibition of cell proliferation and indirectly via inhibition of tumor angiogenesis. In TNBC patient-derived xenograft (PDX) tumor models, the presence of activating Notch mutations/fusions correlated with potent response to AL101 monotherapy. For additional information on nonclinical studies, refer to the Investigator's Brochure.

The current study is designed to evaluate the efficacy and safety of AL101 monotherapy in subjects with Notch-activated recurrent or metastatic TNBC; Notch activation will be determined by a Next Generation Sequencing (NGS) test.

2.2. Background

Breast cancer is the most common cancer diagnosed among US women and is the second leading cause of cancer-related deaths (DeSantis, 2017). TNBC represents 1 of the 4 main molecular subtypes of invasive BC (Tamimi, 2012; Dieci, 2014) accounting for 10-20% of total cases. It is significantly more common in African American premenopausal women and women with a breast cancer type 1 susceptibility gene (BRCA1) mutation (Perou, 2011; Lin, 2012). TNBC is biologically heterogeneous but can be mainly identified by a negative phenotype for the estrogen receptor (ER) and progesterone receptor and a lack of gene amplification/protein overexpression

for the human epidermal growth factor receptor 2 (HER2). These biologic characteristics confer a higher aggressiveness and relapse risk than that observed in all other BC subtypes (Rouzier, 2005; Dua, 2017; Polk, 2017).

Due to the loss of the aforementioned tumor cell receptors, patients with TNBC do not benefit from hormonal therapy or treatments targeting the oncogenic HER2 pathway (Lin, 2012). The standard of care for patients with recurrent and/or metastatic disease is cytotoxic chemotherapy (taxane- or anthracycline-containing regimens for TNBC, and platinum-based chemotherapy for BRCA1/2 mutation-associated TNBC) (Cardoso, 2017), leading to a median survival of approximately 13 months from the time of recurrence or diagnosis of distant metastases (Kassam, 2009; Steponaviciene, 2011). A recent meta-analysis of first line treatment in metastatic TNBC in phase 3 studies reported pooled objective response rate (ORR) of 23%, median overall survival (OS) of 17.5 months, and median progression-free survival (PFS) of 5.4 months with single-agent chemotherapy (Li, 2019).

Currently, two poly (ADP-ribose) polymerase (PARP) inhibitors olaparib and talazoparib are approved for TNBC patients with BRCA mutations. Atezolizumab in combination with nab-paclitaxel was recently approved for programmed death-ligand 1 (PD-L1) - positive locally advanced or metastatic TNBC (Li, 2019; Narayan, 2020).

The Notch signaling pathway has emerged as a potential pathway in the pathogenesis and tumor progression of TNBC. Notch receptors are associated with the regulation of tumor-initiating cells (TICs) behavior, as well as with the etiology of TNBC. There is a strong evidence that the Notch pathway is a relevant player in mammary cancer stem cells maintenance and expansion. In addition, Notch receptors expression and activation strongly correlate with the aggressive clinicopathological and biological phenotypes of BC (e.g., invasiveness and chemoresistance), which are relevant characteristics of TNBC subtype (Giuli, 2019).

2.3. Benefit/Risk Assessment

More detailed information about the known and expected benefits and risks and reasonably expected adverse events of AL101 may be found in the Investigator's Brochure (IB).

2.3.1. Risk Assessment

Potential Risk of Clinical Significance	Summary of Data/Rationale for Risk	Mitigation Strategy
Investigational Product AL101		
Hepatic function abnormalities and drug-induced liver injury (DILI)	Refer to Section 8.3.5.4	Hepatic function will be closely monitored throughout the study. Refer to Section 6.4.3,
Colitis	Refer to Section 8.3.5.1	Signs and symptom of colitis will be closely monitored, Refer to Section 6.4.4.
Anaphylaxis	Refer to Section 8.3.5.2.	In case of Grade 3 or 4 allergic reaction, IP infusion will be stopped

Potential Risk of Clinical Significance	Summary of Data/Rationale for Risk	Mitigation Strategy
	Histamine is a major mediator of anaphylactic/anaphylactoid responses in man, such as those induced by Cremophor EL, an excipient of AL101.	and infusion tubing from the subject will be disconnect. Refer to Section 6.4.1. Glucocorticoids may be administered for treatment of infusion reaction and as premedication to prevent further infusion reaction. Refer to Section 6.6.1.
Keratoacanthoma	Refer to Section 8.3.5.3	Subjects will be closely monitored for skin changes throughout the study. Subjects will be counseled to avoid excessive sun and UV exposure during the study
Study Procedures		
Infusion site reactions	Refer to Section 6.4.1.	Glucocorticoids may be administered for treatment of infusion reaction and as premedication to prevent further infusion reaction. Refer to Section 6.6.1.

2.3.2. Benefit Assessment

Nonclinical and clinical data provide rationale for evaluating the potential clinical benefits of AL101 in subjects with TNBC for whom available standard of care is not providing durable response as defined by complete (CR) or partial response (PR). In a Phase 1 study (CA216003, [NCT01653470](#)), clinical activity of AL101 was shown in an unselected heavily treated patient population with solid tumors; confirmed objective responses were reported for 8 of the 22 subjects (36.4%) with TNBC who were treated with AL101 in combination with various chemotherapy agents (1 subject with a CR and 7 subjects with PR). It is estimated that treatment with AL101 may have a positive impact in patients with Notch-activated recurrent or metastatic TNBC, who may thus derive benefit from this treatment.

2.3.3. Overall Benefit Risk Conclusion

Taking into account the measures taken to minimize risk to subjects participating in this study, the potential risks identified in association with AL101 are justified as compared to the potential benefits that may be afforded to subjects with Notch-activated TNBC.

3. OBJECTIVES AND ENDPOINTS

Objectives	Endpoints
Primary 
 To evaluate the efficacy of AL101 monotherapy in subjects with Notch-activated recurrent or metastatic TNBC 	
 Proportion of subjects who demonstrate an overall response rate (ORR), defined as PR + CR as assessed by investigator based on Response Evaluation Criteria in Solid Tumors (RECIST) v1.1
Secondary 
 Efficacy - Secondary 	
 Clinical benefit response rate (CBR) defined as CR +PR + stable disease (SD) by investigator review based on RECIST v1.1 Duration of response (DOR) by investigator review based on RECIST v1.1 Progression free survival (PFS) Proportion of subjects who have PFS at 6 months Overall survival (OS) Quality of life (QoL) as determined by European Organization for Research and Treatment of Cancer Quality of Life Questionnaire 30 questions (EORTC QLQ-C30) and Breast Cancer 45 questions (EORTC QLQ-BR45)

 To evaluate the safety and tolerability of AL101 monotherapy in subjects with recurrent or metastatic TNBC 	
 Frequency, duration and severity of treatment-emergent adverse events (TEAEs) and serious adverse events (SAEs) Incidence of clinically significant abnormalities in laboratory parameters, electrocardiograms (ECGs), vital signs and physical examination

Objectives	Endpoints
Exploratory 
 • To characterize biomarkers as a measure of response to AL101 monotherapy, and overall prognosis • To establish correlation between positive Notch intracellular domain (NICD) immunohistochemistry (IHC) stain and Notch activating mutations • To establish the correlation between mutations in Notch and associated genes and response or resistance to investigational product 	Endpoints 
 • Change in quantity of circulating tumor cells (CTCs), and other biomarkers in CTCs • Predictive biomarkers of response or resistance to the investigational product will be explored: 
 – IHC: Tumor specimens will be stained for NICD and other potential biomarkers. – NGS: Mutational analysis of tumor tissue samples, and potentially cfDNA and CTCs. – Gene expression analysis in tumor tissue samples.

4. OVERALL STUDY DESIGN

4.1. Study Design

This is an open-label multicenter, Phase 2, Simon two-stage optimal design for targeted therapy study of single arm AL101 monotherapy in subjects with Notch-activated recurrent or metastatic TNBC whose disease has recurred or progressed after 3 or fewer lines of prior therapy.

The design will include a lead-in cohort with 6 subjects to ascertain safety of the investigational product (IP), AL101, 6 mg weekly (QW). The safety will be reviewed on a regular schedule (weekly calls with investigators, and quarterly reviews with the Data Monitoring Committee [DMC]). After the 6th subject is enrolled and completes 4 weeks of therapy (1 cycle), the results will be reviewed in aggregate and, if the safety is acceptable (as defined below), the study will continue at 6 mg administered QW. Note, if safety is not acceptable amongst the first 6 subjects dosed at 6 mg QW, the IP dose will be reduced to 4 mg QW. The decision on which dose to use for the remainder of the study will be determined after formal safety assessment with the investigators and the DMC.

Acceptable safety:

- 2 or fewer subjects experience Grade 3 or 4 diarrhea lasting more than 3 days
- 2 or fewer subjects experience another specific Grade 3 or 4 adverse event (AE) which is attributable to IP

After the lead-in phase with AL101 6 mg QW, the study will proceed to complete the described Simon two-stage design as shown in [Figure 1](#) and described in Section [9.1](#).

Prior to entering the study, to determine eligibility, potential candidates who sign a separate pre-screening informed consent, will undergo pre-screening assessment for evaluation of Notch mutational status from a persistent locally advanced or metastatic lesion. If historical genotyping results from the last 2 years that identify a Notch-activated genetic alteration are available from a commercially available NGS assay or laboratory developed test (LDT), these results are acceptable to use for determining eligibility. In Europe any commercially available CE marked device can be used.

If acceptable genotyping results are not available, testing of a sample collected from a locally advanced or metastatic lesion must be conducted during pre-screening using a commercially available NGS assay, LDT or other validated investigational use only (IUO) clinical trial assay capable of detecting genetic alterations in the *NOTCH 1/2/3/4* genes. For this purpose, tumor biopsy from within the last 2 years or fresh biopsy will be needed.

After signing an informed consent, all subjects will then undergo screening assessments to determine study eligibility over a 28-day Screening period. Eligibility criteria for study entry will be assessed locally by the investigator; radiographic scans at screening and from the prior 12 months will be collected and held for possible future retrospective independent evaluation. Tumor tissue will need to be provided during the Screening period for confirmatory study-specific testing.

Starting on Cycle 1, Day 1, eligible subjects will be treated with IP intravenously (IV) QW, on Days 1, 8, 15 and 22 of each 28-day cycle. Treatment will continue until the occurrence of unequivocal radiographic disease progression per RECIST v1.1 as assessed by the investigator, or clear clinical progression as assessed by the investigator, or unacceptable toxicity, or other reasons for discontinuation.

All subjects will receive premedication with H1- and H2-blockers per institution guideline (refer to Section 6.6.1) and steroids as prophylaxis (refer to Section 6.6.2). Toxicity post-AL101 administration will be managed as specified in Section 6.4.

During the Treatment period, subjects will undergo radiographic assessments every 8 weeks (± 3 days) for review by the investigator. Radiographic scans will also be collected and held for possible future retrospective independent evaluation. Other assessments will be done as specified in the Schedule of Activities (Table 1). A repeat of tumor imaging will be required for the purposes of confirmation of response (i.e., partial response, and/or complete response). The confirmation scan should be no earlier than 4 weeks following the first indication of response.

Samples from tumor biopsies will be collected at screening from a locally advanced or metastatic lesion (fresh or archival within 2 years), and at Cycle 4 Day 1 ± 28 days (provided that biopsy collection is medically safe and not contraindicated). If an archival tumor block or 25 unstained slides are not available, the subject will be required to have a fresh tumor sample obtained at screening. Biopsy samples will be evaluated by NGS for genomics, immunohistochemistry (IHC) for Notch intracellular domain (NICD) stain, and other biomarkers potentially related to sensitivity to AL101 or TNBC prognosis. Blood samples for pharmacokinetics (PK) and biomarker analysis will also be collected on the same day as the on-treatment biopsy.

All subjects will undergo end of study (EOS) visit 30 days post last treatment with IP and will be contacted by phone to determine survival status (refer to Section 4.4). In subjects who discontinued IP due to toxicity, radiographic imaging will be done every 3 months until disease progression or until the subject initiates another anti-cancer therapy.

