The design will include a lead-in cohort with 6 subjects to ascertain safety of the investigational product (IP), AL101, 6 mg weekly (QW). The safety will be reviewed on a regular schedule (weekly calls with investigators, and quarterly reviews with the Data Monitoring Committee [DMC]). After the 6th subject is enrolled and completes 4 weeks of therapy (1 cycle), the results will be reviewed in aggregate and, if the safety is acceptable (as defined below), the study will continue at 6 mg administered QW. Note, if safety is not acceptable amongst the first 6 subjects dosed at 6 mg QW, the IP dose will be reduced to 4 mg QW. The decision on which dose to use for the remainder of the study will be determined after a formal safety assessment with the investigators and the DMC.

Acceptable safety:

- 2 or fewer subjects experience Grade 3 or 4 diarrhea lasting more than 3 days
- 2 or fewer subjects experience another specific Grade 3 or 4 adverse event (AE) which is attributable to IP

After the lead-in phase with AL101 6 mg QW, the study will proceed to complete the described Simon two-stage design as shown in [Figure 1](#) and described in Section [9.1](#).

Prior to entering the study, to determine eligibility, potential candidates who sign a separate pre-screening informed consent, will undergo pre-screening assessment for evaluation of Notch mutational status from a persistent locally advanced or metastatic lesion.

After signing an informed consent, all subjects will then undergo screening assessments to determine study eligibility over a 28-day Screening period, including TNBC molecular characterization. Eligibility criteria for study entry will be assessed locally by the investigator; radiographic scans at screening and from the prior 12 months will be collected and held for possible future retrospective independent evaluation.

Starting on Cycle 1, Day 1, eligible subjects will be treated with IP intravenously (IV) QW, on Days 1, 8, 15 and 22 of each 28-day cycle. Treatment will continue until the occurrence of unequivocal radiographic disease progression per RECIST v1.1 as assessed by the investigator, or clear clinical progression as assessed by the investigator, or unacceptable toxicity, or other reasons for discontinuation.

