4.3. Justification for Dose

The dose selected for this study (6 mg QW) is based on nonclinical studies, prior clinical studies conducted by BMS (the previous developer) (CA216001, CA216002 and CA216003) and preliminary outcome from the ongoing ACCURACY study conducted by Ayala (NCT03691207). Please also refer to the Investigator's Brochure for further information.

Study CA216001 was a first in human dose escalation study which evaluated doses ranging from 0.4 mg QW to 8.4 mg QW. In the initial dose-escalation, there were no dose limiting toxicities (DLTs) noted in 4 subjects at 6 mg QW. Dose escalation was continued to 8.4 mg QW and DLTs, including a Grade 5 liver failure in one subject, were noted. The case of liver failure was complicated by pre-existing liver injury and possible contribution of an investigational nucleoside analogue, the subject had previously received, known to cause delayed liver toxicity. Consequently, an additional 10 subjects were enrolled at the 6 mg QW dose. There were 4 DLTs observed amongst 4 of these additional subjects including 2 subjects with Grade 3 diarrhea, 1 subject with Grade 3 vomiting/Grade 3 lipase elevation, and 1 subject with Grade 3 large intestinal ulcer with a non-treatment related Grade 3 infectious colitis. Based on this data, the previous sponsor assessed the RP2D as 4 mg QW.

However, upon careful review of these data, Ayala concluded that, with proper control of diarrhea, 2 of the DLTs which were noted at 6 mg QW could probably have been controlled so that they were potentially not DLTs. Importantly this is further substantiated by the observation in the ongoing ACCURACY study that (AL-ACC-01), with proactive control of diarrhea, there was only a 3% (2/34) incidence of Grade 3 diarrhea as opposed to the 19% (8/43) incidence noted in CA216001. The proactive control of diarrhea is delineated below and includes frequent and early use of loperamide followed by a low threshold to use steroids.

Furthermore, study CA216002 evaluated subjects with T-ALL/T-LL at the 6 mg QW dose. The subjects in this study tolerated the 6 mg QW dose well with no reported DLTs.

From a mechanistic perspective interest in using the higher dose of AL101 is driven by PK and pharmacodynamic (PD) results from the Phase 1 Study CA216001 indicate that AL101 exposure (C_{max} and area under the curve [AUC]) increases with approximately linear kinetics for QW

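### The lead-in safety definition limits event types but not affected subjects, so 4 of 6 subjects with the earlier 6 mg DLT pattern would count as acceptable

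*Combined protocol and SAP*

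**What the plan says.** Section 4.1, repeated in the Synopsis (1.1), treats 6 lead-in subjects at 6 mg QW and reviews them together once the sixth has completed one 4-week cycle. Two conditions define acceptable safety: "2 or fewer subjects experience Grade 3 or 4 diarrhea lasting more than 3 days" and "2 or fewer subjects experience another specific Grade 3 or 4 adverse event (AE) which is attributable to IP". The stated consequence is that "if the safety is acceptable (as defined below), the study will continue at 6 mg administered QW"; otherwise the dose drops to 4 mg. The same paragraph says the dose for the rest of the study is "determined after formal safety assessment with the investigators and the DMC". Neither section limits the number of subjects with any qualifying event, and neither names Grade 5.

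Section 4.3 gives the earlier experience at this dose in CA216001. In escalation, "there were no dose limiting toxicities (DLTs) noted in 4 subjects at 6 mg QW". Ten more subjects were then treated at 6 mg: "There were 4 DLTs observed amongst 4 of these additional subjects including 2 subjects with Grade 3 diarrhea". The other two were one subject with Grade 3 vomiting and lipase elevation, and "1 subject with Grade 3 large intestinal ulcer with a non-treatment related Grade 3 infectious colitis". The previous sponsor set the recommended dose at 4 mg. The current sponsor argues that with proper diarrhea control "2 of the DLTs which were noted at 6 mg QW could probably have been controlled". In support it gives Grade 3 diarrhea rates of 3% (2/34) in ACCURACY and 19% (8/43) in CA216001; later in the section the same comparison appears as 3.4% and 19.1%.

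**The concern.** A rule that counts each event type separately reacts when toxicity clusters in one type. It hardly reacts when toxicity is spread over several types, and that is how the 6 mg DLTs appeared in CA216001. The sponsor's argument for returning to 6 mg addresses the two diarrhea cases; the diarrhea rates say nothing about the other two. The lead-in sets the dose for up to 67 − 6 = 61 further subjects, and Stage 2 enrolls while Stage 1 matures. A written label of acceptable on a cohort with 4 of 6 subjects affected would be a poor starting point for the dose review.

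**Working it through.** **Does the earlier pattern pass?** Suppose four of six lead-in subjects have the CA216001 events, with both diarrhea cases lasting over 3 days and the ulcer judged attributable. By type the counts are 2, 1 and 1, and none exceeds 2. If the second condition is read as pooling all non-diarrhea events, the counts are 2 and 2, and again neither exceeds 2. Both readings give acceptable with 4/6 = 67% affected. If the ulcer is not attributable, 2 + 1 = 3 of 6 remain, and the criteria are still met.

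**How often?** The protocol gives no operating characteristic for the lead-in rule, so there is none to reproduce. Inputs from Section 4.3: 4 DLT subjects of 4 + 10 = 14 at 6 mg (28.6%), or 4 of the 10 added later (40%), split 1/2 diarrhea, 1/4 vomiting/lipase, 1/4 ulcer. Assumptions: the old rates carry over unchanged, each subject has at most one event type, only these types occur, and diarrhea lasts over 3 days.

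Let X be the number affected, binomial(6, q). The share of outcomes with X = x that meet the criteria depends only on the split:

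- By type: x = 3: 1 − (1/8 + 1/64 + 1/64) = 0.844; x = 4: 0.586; x = 5: 0.293; x = 6: 0.088.
- Pooled (1/2, 1/2): x = 3: 1 − 2/8 = 0.750; x = 4: 6/16 = 0.375; x = 5 or 6: 0.

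At q = 0.40, P(X=3) = 20 × 0.4³ × 0.6³ = 0.2765, P(X=4) = 0.1382, P(X=5) = 0.0369, P(X=6) = 0.0041.

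- By type: 0.2333 + 0.0810 + 0.0108 + 0.0004 = 0.325.
- Pooled: 0.2074 + 0.0518 = 0.259.

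At q = 4/14, P(X=3) = 0.1700, P(X=4) = 0.0510, P(X=5) = 0.0082, P(X=6) = 0.0005.

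- By type: 0.1434 + 0.0299 + 0.0024 + 0.0000 = 0.176.
- Pooled: 0.1275 + 0.0191 = 0.147.

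| Probability that the criteria are met and: | 4/14 rates | 4/10 rates |
|---|---|---|
| 3 or more of 6 affected, by type | 17.6% | 32.5% |
| 3 or more of 6 affected, pooled | 14.7% | 25.9% |
| 4 or more of 6 affected, by type | 3.2% | 9.2% |
| 4 or more of 6 affected, pooled | 1.9% | 5.2% |
| 3 or more of 6, by type, ulcer not counted | 6.9% | 14.1% |
| 3 or more of 6, by type, all rates halved | 3.4% | 7.9% |

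**Rates in Section 4.3.** 2/34 = 5.9%, while 1/34 = 2.9%, so the printed 3% does not match its own count. The later 3.4% does not match 2/34 either; it would fit 1/29, and 29 is the ACCURACY safety set quoted there. 8/43 = 18.6%, which rounds to 19% but not to 19.1%. The later sentence gives no counts, so a different data cut is possible (9/47 is also 19.1%).

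**The case against.** The strongest reply is that the criteria are not the only gate. Results are reviewed in aggregate, and the dose is set after a formal assessment by investigators and DMC, who may choose 4 mg whatever the counts. Section 9.5 also places stopping rules in a DMC charter that is not among the documents, so a subject-level trigger may exist there. This stands as a limit on the consequence. It does not repair the protocol, whose own definition labels the pattern acceptable and ties continuation at 6 mg to that label.

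Second, the old rates are pessimistic. All four DLT subjects had gastrointestinal events, and the steroid premedication and diarrhea measures are aimed at gastrointestinal toxicity. CA216002 reported no DLTs at 6 mg. The 4/10 rate also leaves out four DLT-free subjects at the same dose. This stands, and the halved-rate row shows how far the size falls.

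Third, 6 mg is only a starting dose. Table 3 modifies or stops dosing for individuals, Section 7.2 interrupts dosing for related serious reactions, and the DMC can recommend stopping at any time. This also stands, but those provisions manage individuals or later events; they do not define when the lead-in cohort supports 6 mg.

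Fourth, a binding step-down on any attributable Grade 3 or higher event could force 4 mg because of transient, manageable toxicity, and its true rate is unknown. This is accepted, and it is why the remedy below triggers a decision rather than dictating a dose.

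**Conclusion.** The gap is real on either reading of the second condition: the definition calls 4 of 6 subjects with the known 6 mg DLT pattern acceptable. Its size is the joint probability that 3 or more of 6 are affected and the criteria are met: 14.7% to 17.6% at the 4/14 rates and 25.9% to 32.5% at the 4/10 rates, as a worst case under the assumptions listed. For 4 or more of 6 it is 1.9% to 9.2%.

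A reader might infer more than the documents support:

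- That the trial would go on at 6 mg with most lead-in subjects affected. The figures describe the written criteria, not the dose decision, which passes through the investigator and DMC assessment.
- That the overall chance of meeting the criteria (94.6% and 87.0% by type) measures the fault. Most of that is lead-ins with 2 or fewer subjects affected, where passing is the intended result.
- That 6 mg is shown to be unsafe, or that the percentage errors overturn the diarrhea argument. Neither follows: at 5.9% against 18.6% the comparison keeps its direction.

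The Section 4.3 mismatch is a separate, minor correction. Only the 2/34 entry is demonstrably inconsistent with its own count; 3.4% and 19.1% can only be flagged for checking.

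**What to change.** Keep both conditions in Sections 4.1 and 1.1 and add a third: safety is not automatically acceptable if 3 or more of the 6 subjects have, during the lead-in review period, any IP-attributable event that is

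- Grade 3/4 diarrhea lasting more than 3 days;
- another Grade 3 or higher event requiring dose modification or discontinuation under Table 3, hematologic events included and supplement-managed electrolyte abnormalities excluded; or
- Grade 5.

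In that case the formal investigator and DMC assessment must decide explicitly between 6 mg and 4 mg, using the subject-level count. If the lead-in is already complete, give the DMC that count.

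This costs one line and no added visits or assessments. The trigger fires with probability P(X ≥ 3 of 6) = 1.6%, 9.9%, 25.6% and 45.6% at true subject-level rates of 10%, 20%, 30% and 40%. The true rate under this definition is unknown and may exceed the earlier DLT rate. When it fires, the cost is an explicit DMC decision and a possible move to 4 mg, with a smaller Hes1/Hes4 reduction and up to 6 more subjects (73 instead of 67).

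In Section 4.3, correct the 2/34 entry (the percentage or the count), verify 3.4% and 19.1% against source, and state the dose and data cut-off behind each rate.
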